8. ASSESSMENT OF SAFETY

8.1 Definitions of Safety Parameters

8.1.1 Unanticipated Problems

The Office for Human Research Protections (OHRP) considers unanticipated problems involving risks to subjects or others to include, in general, any incident, experience, or outcome that meets all of the following criteria:

- unexpected in terms of nature, severity, or frequency given (a) the research procedures that are described in the protocol-related documents, such as the IRB-approved research protocol and informed consent document; and (b) the characteristics of the subject population being studied;
- related or possibly related to participation in the research (possibly related means there is a reasonable possibility that the incident, experience, or outcome may have been caused by the procedures involved in the research); and
- suggests that the research places subjects or others at a greater risk of harm (including physical, psychological, economic, or social harm) than was previously known or recognized.

8.2 Specification of Safety Parameters

Safety monitoring for this study will focus on unanticipated problems involving risks to participants.

8.3 Reporting Procedures

8.3.1 Unanticipated Problem Reporting

Per National Dental PBRN procedures, unanticipated incidents and events will be reported to the PIs. After the PIs is made aware of the incident/event, the following procedures will be followed.

Incidents or events that meet the OHRP criteria for unanticipated problems require the creation and completion of an unanticipated problem report form. OHRP recommends that investigators include the following information when reporting an adverse event, or any other incident, experience, or outcome as an unanticipated problem to the IRB:

- appropriate identifying information for the research protocol, such as the title, investigator's name, and the IRB project number;
- a detailed description of the adverse event, incident, experience, or outcome;

- an explanation of the basis for determining that the adverse event, incident, experience, or outcome represents an unanticipated problem;
- a description of any changes to the protocol or other corrective actions that have been taken or are proposed in response to the unanticipated problem.

To satisfy the requirement for prompt reporting, unanticipated problems will be reported using the following timeline:

- Unanticipated problems will be reported to the IRB as soon as possible but in all cases within 10 working days of the investigator becoming aware of the problem.
- All unanticipated problems should be reported to appropriate institutional officials (as required by an institution's written reporting procedures), the supporting agency head (or designee), and OHRP within one month of the IRB's receipt of the report of the problem from the investigator.

All unanticipated problems will be reported to NIDCR concurrently with reporting to the IRB. These reports will be made to NIDCR's centralized reporting system via the Clinical Research Operations and Management Support (CROMS) contractor.

- Product Safety Fax Line (US): [name]
- Product Safety Fax Line (International): [contact]
- Product Safety Email: [contact]

9. STUDY OVERSIGHT

The PIs will be responsible for study oversight, including monitoring safety, ensuring that the study is conducted according to the protocol and ensuring data integrity. The NCC will provide the PIs with current data summaries, and the PIs will review the data for safety concerns and data trends at regular intervals, and will promptly submit reportable events to the IRB and NIDCR that arise during the conduct of the study, per the IRB's reporting time-frame requirements. To ensure data integrity, the PIs, NCC, and study team will adhere to data quality management processes (please see Section 13).

10. CLINICAL SITE MONITORING

No outside clinical site monitoring will be employed for this study. The NCC is responsible for launching the study and collecting data received as part of the study. Quality Assurance/Quality Control activities associated with data collection and processing will be developed by the NCC. The NCC will ensure that the quality and integrity of the study data and data collection are maintained. The NIDCR reserves the right to conduct independent clinical site monitoring as necessary.

11. STATISTICAL CONSIDERATIONS

11.1 Study Hypotheses

The observational CARAD study is exploratory in nature. The study objectives do not include testing specific hypotheses, but rather the research is hypothesis-generating to identify important barriers, facilitators, and other issues guiding dental practitioners' willingness and readiness to provide COVID-19 vaccines (and other vaccines) at dental office visits.

11.2 Final Analysis Plan

Analysis plans. Qualitative and quantitative surveys and analyses will be conducted using practitioner qualitative interview and survey response data.

Practitioner interviews. We will conduct interviews by telephone, and verbal consent will be obtained at the start of the call. An interview guide will be developed based on the Diffusion of Innovations Model (24,25) to assess barriers and facilitators to acceptability, appropriateness, and feasibility of a COVID-19 vaccine delivery program for dental office patients. The Diffusion of Innovations Model proposes that there are several key factors influencing the adoption of innovations in service organizations: characteristics of the adopters (e.g. psychological antecedents and nature of the adoption decisions) and assimilation by the organization, features of the inner context (organizational readiness and antecedents) and outer context (e.g. political directives), influences by opinion leaders.

The interview guide will include questions about experiences with administering the COVID-19 and other vaccines, vaccine delivery workflows in general, perceptions about skills, knowledge and support required to administer the vaccine, and factors that may influence their willingness and interest in administering such a vaccine (including vaccine hesitancy).

Analyses of qualitative data. All recordings will be transcribed by a professional transcriptionist and analyzed using NVivo software. Transcripts will be analyzed following a template analysis. Template analysis is a form of thematic analysis that relies on a formalized coding template. It combines the use of a priori themes (concepts outlined above in the data collection section) with topics that emerge during data review and therefore offers flexibility to capture themes of interest to researchers as well as themes that emerge as relevant to participants during the data collection process. Defining themes both a priori and as they emerge will let us appropriately answer the research question as well as capturing issues that emerge from the interviews.

Analyses of quantitative survey data. We will estimate the mean proportions of practitioners who: a) report the likelihood that their patients are interested/very

perceived to be vaccinated for the coronavirus at a dental office visit; b) report acceptable/very acceptable levels of dental providers' role in preventing SARS-CoV-2 transmission through vaccination; c) report they are confident/very confident in their ability to deliver vaccines at dental office visits; d) report they are confident/very confident their dental practice can manage COVID-19 vaccine supplies with access to adequate temperature control (refrigeration and freezing); and e) report they are willing/very willing to provide COVID-19 vaccines to their patients if known barriers can be overcome. Mean proportions and 95% confidence internals for each dichotomous outcome will be measured from responses to 5-point Likert scale assessments. We will compare proportions by practitioner type (general dentist, specialists involved with routine care delivery), practice setting (e.g., solo/small group, large group, integrated health system, etc.), practice location, and dentist characteristics. Multivariable logistic regression modeling of outcomes a-e will be conducted if mean proportions differ across multiple factors.

We use the theory of planned behavior (TPB) as a conceptual model for evaluating individual's intentions to perform a given activity as well as actual performance of the activity.²⁵ The TPB posits that behavioral intentions are influenced by the interplay of the individual's attitudes toward the activity, subjective norms, or expectations, to perform the activity, and their perceived level of control over the performing the activity. These factors influence intentions which then predict actual future performance of the activity. Perceived control over the activity also has a direct influence on performance independent of intentions. The TPB has been used to understand medical and dental practitioner's treatment decisions.^{26–29} However, the dental provider's behavior has not been extensively studied.

For this study, *acceptability* is reflected in respondents': a) *personal attitudes* about vaccine safety and effectiveness and receiving vaccinations; b) *professional attitudes* about the roles of the dental profession in general and their individual decisions in particular to promote and deliver vaccines; c) practitioners' perceptions of their patients attitudes about receiving vaccinations; and d) *perceived social norms* reflecting social expectations to provide vaccine recommendations and vaccinations. *Readiness* is reflected in respondents': a) *perceived behavioral control* over vaccine promotion and delivery, including patient demand, regulatory and organizational constraints, supply management and other economic constraints; b) receipt of necessary training; c) *behavioral intentions* to promote and deliver vaccines; and d) having direct experience promoting or delivering vaccines to patients.

Attitudes. We will capture data on practitioners' personal positive and negative attitudes about vaccine safety and effectiveness, and professional attitudes about vaccine advice and delivery to patients. The survey includes 29 questions assessing practitioner attitudes. *Personal perceptions* about vaccinations are captured using 7

questions (the short version) of the 5C model, a validated instrument developed by Betsch and colleagues (2018) ³⁰ measures an individual's confidence, constraints, complacency, calculation, and collective responsibility related to receiving vaccinations. We include 13 questions measuring practitioners' professional attitudes about vaccination, and 9 questions adapted 5C questions to measure practitioner beliefs about their patient attitudes about vaccinations.

Subjective norms. We use 12 questions to capture information about practitioners' perceptions of social pressures to recommend and/or provide vaccinations, in general and for COVID-19 disease. We assess perceived pressure from patients, organizations/employers (excluding private practitioners), and professional organizations to recommend or provide vaccinations. We also ask if other local practitioners provide vaccines to their patients.

Perceived behavioral control. We use 25 questions to capture information about practitioners perceived level of control over vaccine recommendations. Control measures include beliefs about their current abilities to provide recommendations and vaccines, comfort providing vaccine counseling, access to training and support, ability to manage supplies, and whether practitioners have sufficient time, patient demand, and compensation. We also assess knowledge about practitioners' state authorization to provide vaccines, ability to explain differences between the mRNA and adenovirus COVID-19 vaccines. We also capture whether changes in these conditions could impact their willingness to provide recommendations and or vaccinations. We assess COVID-19 vaccinations separately from other approved vaccinations.

Practitioner characteristics. We collect practitioner and practice characteristics from the enrollment questionnaire, including age, gender, race, ethnicity, practice type, practice setting, practice region, and state location. We also collect state level COVID-19 policy stringency and case and death rate data for use with the COVID-19-related analyses. We also collect survey data for: a) practice setting; b) rural, suburban, and urban location; and c) whether the practice is located in a healthcare provider shortage area (HPSA).

Behavioral intentions and behavior. *Behavioral intentions* and captured by questions representing practitioners' receipt of training certification to provide vaccines, and their stated willingness to recommend and/or provide vaccines. Vaccine behavior is assessed using self-reported provision of vaccine recommendations or vaccinations for patients. For vaccine delivery, we capture information about providing vaccines through external community organization and/or for their patients at dental offices. We ask separately about vaccinations in general and COVID-19 specifically.

Sample size and power for primary outcome. The design of the qualitative components of the study involve small numbers of patients and practitioners and are developmental in nature. For the quantitative dentist survey (n= about 500), assuming equal group sample size of 100 respondents and a response rate of 0.2 in the reference group, we will be able to detect a difference in proportions of 0.176 (i.e., 0.376 response rate in the comparison group) to achieve 80% power. Alternatively, to detect a difference of 0.2 between the two groups with a response rate of 0.2 in the reference group, we'll need a sample size of 79 dentists per group.

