3.2 Secondary

Objectives	Brief Description/Justific ation of Outcome Measure	Outcome Measured By	Time Frame
Assess levels of acceptability and readiness to participate in alternative COVID-19 vaccine delivery programs, and other vaccine programs, through dental offices, by practitioner and practice characteristics, and accounting for relevant vaccine supply management and legislative factors	Assessing dental practitioners' interest and ability to participate in a large public health effort to vaccinate the U.S. population requires an assessment of salient barriers, ability, and willingness to accept this role.	Outcomes will be assessed using dichotomous categories from 5-point Likert scale responses for: a) level of acceptability of dental providers' role in preventing SARS-CoV-2 transmission through vaccination; b) level of relevance of vaccine delivery for my dental practice; c) level of perceived interest among my dental patients; d) level of confidence for managing vaccine supplies; and e) level of confidence for delivering vaccines at dental office visits. COVID-19, HPV,	Online surveys (and retests) are conducted over about 6-8 weeks. Practitioner's Demographic and practice characteristics are obtained from the Network's Practitioner Database

and flu vaccine delivery will be assessed.	
A target of 25-30 test- retests will be conducted to assess item internal validity.	

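### The only adjusted analysis for Objective 2 is run only if crude proportions differ across several factors, so the promised accounting for supply and legislative factors may never be done

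*Protocol*

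**What the plan says.** Objective 2, in section 3.2 and again in the Protocol Summary, is to assess acceptability and readiness "by practitioner and practice characteristics, and accounting for relevant vaccine supply management and legislative factors". No condition is attached.

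Section 11.2 sets out the survey analysis in three steps. First come proportions with 95% confidence intervals for dichotomised outcomes a-e. Next come crude comparisons: "We will compare proportions by practitioner type (general dentist, specialists involved with routine care delivery), practice setting", followed by practice location and dentist characteristics. Last comes the adjusted step: "Multivariable logistic regression modeling of outcomes a-e will be conducted if mean proportions differ across multiple factors". The protocol describes no other adjusted analysis.

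Section 11.2 also says: "We also collect state level COVID-19 policy stringency and case and death rate data for use with the COVID-19-related analyses". The survey collects items on supply management and on knowledge of state authorisation to vaccinate. The protocol describes no adjusted analysis that would use these data outside the conditional model.

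**The concern.** To account for supply and legislative factors when comparing levels by practitioner or practice characteristic is, on its ordinary reading, an adjusted comparison. Section 11.2 lets the crude results decide whether that comparison is made.

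Crude differences are a poor guide to whether adjustment is needed. Setting, location, region and state law are likely to be correlated. If a characteristic that raises willingness is less common where another favourable condition holds, the two associations partly cancel in the crude table. The condition then fails in the very case where adjustment would show something. It also fails if exactly one factor differs, however large that difference is.

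At stake are the stated content of Objective 2 and the study's aim of identifying barriers and facilitators.

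**Working it through.** **1. The passages side by side.** Objective 2 promises accounting for supply and legislative factors, without condition. The crude comparisons cover practitioner type, setting, location and dentist characteristics, with no supply or legislative factor named. The multivariable model is the only other comparison, and it is conditional. So if the condition is not met, no described comparison delivers that part of Objective 2. This step needs no assumption about the data.

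**2. The plan's own power figures.** The inputs are "assuming equal group sample size of 100 respondents and a response rate of 0.2 in the reference group" and "we will be able to detect a difference in proportions of 0.176 (i.e., 0.376 response rate in the comparison group) to achieve 80% power". Two-sided alpha of 0.05 is assumed, because section 11.2 states none. With unpooled variance, n per group = (1.960 + 0.842)² × [p1(1−p1) + p2(1−p2)] / d².

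- 0.2 vs 0.4: 7.849 × (0.16 + 0.24) / 0.04 = 78.5, so 79 per group, as stated.
- 0.2 vs 0.376: 7.849 × (0.16 + 0.2346) / 0.0310 = 100 per group, as stated.

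The figures reproduce and are not in dispute. They are used below only to show how often the condition could fail.

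**3. The condition at the planned power.** Read *differ* as p<0.05 (an assumption).

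- Only two factors screened, both true, independent, each at 80% power: both pass with probability 0.8 × 0.8 = 0.64, so the model is skipped in 36% of studies.
- The same with 0.2 vs 0.3 and 100 per group (power 37%): 0.37 × 0.37 = 0.14.
- One true factor at 80% power among k factors, the rest null: P(at least two pass) = 0.8(1 − 0.95^(k−1)) + 0.2(1 − 0.95^(k−1) − (k−1) × 0.05 × 0.95^(k−2)). For k = 4, 6 and 8 this gives 0.12, 0.19 and 0.25.

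**4. Negatively correlated factors.** The simulation assumed n=500, two binary factors each at 40% prevalence with correlation −0.32, both true odds ratios 1.8, a baseline rate of 0.25, and 2000 replicates. The crude odds ratio averages about 1.48. Each crude test has about 54% power, against about 82% in the adjusted model. The share of studies in which at least two factors pass, so that the model is run, is:

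| Factors screened | Model triggered |
|---|---|
| These two only | 21-24% |
| Plus 4 independent null factors | 35-38% |
| Plus 1 further true factor (OR 1.8) and 4 null | 80-81% |
| Plus 2 further true factors (OR 1.8) and 4 null | 95-96% |

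The ranges are from repeated runs. With two uncorrelated factors and nothing else screened, the model is triggered in about 74%.

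**5. Complete masking.** Assume a factor held by half of 500 respondents, a covariate with odds ratio 3 that is unevenly spread between the two halves, and a crude rate of 0.20 in both. Only these two are screened. The lost share is the proportion of runs in which the adjusted effect is significant but the model would not have been run.

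| Covariate present in the two halves | Adjusted OR of the factor | Crude screen flags the factor | Lost share |
|---|---|---|---|
| 30% / 70% | 1.55 | 5% | 38% |
| 35% / 65% | 1.39 | 5% | 26% |
| 40% / 60% | 1.24 | 4% | 12% |

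**The case against.** **Many factors are screened, not two.** This stands in large part. Section 11.2 lists several characteristics, and step 4 shows that with a few real associations among them the model would nearly always be run. The 21-24% figure is close to a worst case and should not be quoted alone.

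***Differ* is undefined, and no significance test is prescribed.** This stands as a limit on the figures. A statistical analysis plan may define the term, and section 15.3 refers the content of the final reports to a separate procedure. But the conditional rule itself is fixed in the protocol and conflicts with the protocol's own objective, however the term is defined.

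**The study is exploratory.** Section 11.1 says so: "The observational CARAD study is exploratory in nature". That lowers the stakes. It does not remove the objective, and a search for barriers and facilitators is poorly served by a rule that can set aside masked associations.

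**Accounting for these factors need not mean regression.** Confidence in managing supplies is itself outcome d, and outcome e asks about willingness once barriers are overcome. Both touch the topic descriptively. Neither adjusts a comparison between types of dentist or practice.

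**Stronger readings that do not hold.**

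- A reader might infer that a null factor will look important in a crude table and never be adjusted. In a two-factor simulation with one null factor and one with odds ratio 2.0, at correlation +0.41, the null factor is flagged in about 30% of runs. The model is also run in about 29-30%, and the null factor is flagged without the model being run in under 1%. There the rule does its job.
- A reader might infer that some outcomes will certainly be reported adjusted and others crude. Section 11.2 speaks of outcomes a-e together and does not say that the condition is applied to each one separately. Mixed reporting is possible, not certain.
- A reader might infer about 100 events from a rate of 0.2 in 500 dentists. That 0.2 is the assumed rate in the reference group only; the comparison group is put at 0.376.

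**Conclusion.** The point holds in a limited form. As written, the protocol can leave part of Objective 2 undone, and it can miss associations that negative confounding hides in crude comparisons. The first conclusion follows from the text alone. The second is a possibility whose frequency the documents do not fix: under the stated assumptions the model is run in anything from about 21% to 96% of studies, depending mainly on how many true factors are screened. This should be corrected because the remedy is simple. It does not undermine the survey, its descriptive proportions or its power figures.

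**What to change.** Delete the condition in section 11.2. State that a prespecified multivariable logistic model will be fitted for each of outcomes a-e whatever the crude comparisons show, with crude and adjusted estimates and 95% confidence intervals side by side.

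Choose a short covariate set in advance from data already collected: practitioner type, setting, location, key dentist characteristics and a state legislative or policy measure. Size it to the number of events observed, counting every level of multi-category factors, or use penalised estimation. Section 2.2 notes that a federal amendment enabled dentists to deliver COVID-19 vaccines, so check that the legislative measure chosen actually varies for the COVID-19 outcomes.

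Add the supply-management measure only where it is neither the outcome nor part of the construct being modelled, for example in a second model. Section 11.2 treats supply constraints as part of readiness, and routine adjustment could remove what is being studied.

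The cost is a sentence or two in the protocol, a few extra model runs, and somewhat wider intervals for some adjusted estimates. No new data are needed.

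### Section 11.2 brings state-level covariates into the COVID-19 analyses but names only logistic regression, with no handling of within-state correlation

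*Protocol*

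**What the plan says.** The secondary objective (Section 3.2, Objective 2) is to assess acceptability and readiness while "accounting for relevant vaccine supply management and legislative factors".

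Under practitioner characteristics, Section 11.2 lists enrollment-questionnaire items that include "practice type, practice setting, practice region, and state location". It then adds: "We also collect state level COVID-19 policy stringency and case and death rate data for use with the COVID-19-related analyses".

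The model is given in the same section: "Multivariable logistic regression modeling of outcomes a-e will be conducted if mean proportions differ across multiple factors". Of those five outcomes, a, b, d and e concern coronavirus or COVID-19 vaccination; c concerns vaccine delivery in general.

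The sample size paragraph begins "For the quantitative dentist survey (n= about 500), assuming equal group sample size of 100 respondents". It contains no design effect. No section mentions clustering, an ICC, a state or random effect, or a robust variance.

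**The concern.** Policy stringency and case and death rates are constant within a state. For their coefficients the amount of information is governed largely by how many states are represented, not by the roughly 500 dentists. Dentists in one state may also share influences that the survey does not measure, such as vaccine rollout or local professional norms. Logistic regression with model-based standard errors ignores that shared variation and credits a state-level covariate with 500 independent observations.

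The stake is the precision claimed for policy and legislative factors. These are named in Objective 2, and the protocol summary promises insight into legislative barriers. With intervals that are too narrow, chance differences between states look like signals.

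**Working it through.** **1. The plan's own figures.** Section 11.2 says "we will be able to detect a difference in proportions of 0.176 (i.e., 0.376 response rate in the comparison group) to achieve 80% power" with 100 per group and a reference rate of 0.2, and that for a difference of 0.2 "we'll need a sample size of 79 dentists per group". Assume a two-sided 5% level (the protocol does not state it) and the unpooled formula n = (z₀.₉₇₅ + z₀.₈₀)² [p₁(1−p₁) + p₂(1−p₂)] / d², with (1.960 + 0.842)² ≈ 7.849:

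- 0.2 vs 0.4: 7.849 × (0.16 + 0.24) / 0.04 = 78.5, so 79.
- 0.2 vs 0.376: 7.849 × (0.16 + 0.2346) / 0.0310 = 100.0.

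Both figures reproduce. Both are calculations for independent dentists.

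**2. Design effect for a purely state-level covariate.** Inputs: N = 500 (protocol); number of states S and ICC (assumed); equal state sizes, m = 500/S. Formulas: DE = 1 + (m − 1) × ICC; ordinary SE / true SE = 1/√DE; actual two-sided error = 2[1 − Φ(1.96/√DE)].

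Example, S = 50 and ICC = 0.05: m = 10; DE = 1 + 9 × 0.05 = 1.45; SE ratio = 0.83; 1.96 × 0.83 = 1.63; error = 10.4%.

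| States | ICC | DE | SE ratio | Actual error |
|---|---|---|---|---|
| 50 | 0.01 | 1.09 | 0.96 | 6.0% |
| 50 | 0.02 | 1.18 | 0.92 | 7.1% |
| 50 | 0.05 | 1.45 | 0.83 | 10.4% |
| 50 | 0.10 | 1.90 | 0.73 | 15.5% |
| 20 | 0.01 | 1.24 | 0.90 | 7.8% |
| 20 | 0.02 | 1.48 | 0.82 | 10.7% |
| 20 | 0.05 | 2.20 | 0.67 | 18.6% |
| 20 | 0.10 | 3.40 | 0.54 | 28.8% |

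**3. Simulation.** 500 dentists, a state-level covariate with no effect, ICC on the latent logistic scale, ordinary logistic Wald test at 5%. Rejection rates in %:

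| Setting | ICC 0 | 0.01 | 0.02 | 0.05 | 0.10 |
|---|---|---|---|---|---|
| 50 states, continuous covariate, unequal sizes (1500 runs) | 5.5 | 5.6 | – | 10.4 | 14.3 |
| 50 states, binary covariate, size CV 1, outcome rate 0.3 (1500 runs) | 4.2 | – | 8.1 | 13.3 | 18.7 |
| 50 states, half with the covariate, unequal sizes (3000 runs) | 4.7 | – | 9.3 | 13.0 | 19.2 |
| 50 states, further set | 4 | 6 | 8 | 14 | 17 |
| 20 states, continuous covariate, unequal sizes (1500 runs) | 4.5 | 8.5 | – | 18.3 | 28.5 |
| 20 states, further set | 5 | 10 | 12 | 19 | 34 |

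With 1500 runs, the Monte Carlo standard error near 5% is √(0.05 × 0.95/1500) = 0.6 points. The simulations and the formula differ in ICC scale and in state sizes, so they agree in order of magnitude rather than cell by cell. Over ICC 0.01-0.10 the simulated error runs from about 6 to 19% with 50 states and from about 9 to 34% with 20.

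**4. Dentist-level covariates.** Their design effect is roughly 1 + (m − 1) × ICC(outcome) × ICC(covariate). This stays near 1 when the covariate varies mostly within states.

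**5. Do clustered standard errors suffice?** With the covariate spread over many of 50 states, they rejected in about 6-8%. With 20 states the rate was about 10%, and with only 3 of 50 states exposed it was 27-29%. Plain clustering is therefore not a safe default for a law that few states have.

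**The case against.** The strongest objection is that the protocol states nothing wrong. A reader might infer that it prescribes ordinary logistic regression with dentists treated as independent. It does not: naming logistic regression rules out neither a state random intercept nor a clustered variance. The choice between them is often left to a SAP, which is not shown here, and Section 15.3 defers the content of the final reports to a Statistical Analysis Standard Operating Procedure. State location is collected, so every option stays open. This part stands and limits the point to a conditional one. It does not remove it. The section is headed as the final analysis plan, it commits these variables to the analyses, and the only variance reasoning it shows assumes independence.

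A reader might also infer that scope-of-practice law is one of the listed state-level covariates. The sentence in Section 11.2 lists only policy stringency and case and death rates. Legislative factors come from the objective, and part of that content is measured per respondent, such as knowledge of state authorization and perceived regulatory constraints. Section 2.2 also reports a federal amendment of March 2021 enabling dentists to give COVID-19 vaccines. So the point reaches legislation only if a state-level legislative variable is actually used.

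The comparison sentence, "We will compare proportions by practitioner type (general dentist, specialists involved with routine care delivery), practice setting", continues with practice location and dentist characteristics and does not list state policy or case rates. If these enter only as adjustment terms, their own intervals are not the main result. That lowers the importance.

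Finally, Section 11.1 calls the study exploratory and without specific hypotheses to test, and the regression is itself conditional. That also stands. Even so, Section 11.2 promises 95% intervals and lets observed differences trigger the modelling, so the width of intervals still matters.

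**Conclusion.** The concern holds in conditional form. State-level covariates are planned, the one regression named comes with no treatment of within-state correlation, and ordinary model-based standard errors would understate the uncertainty of state-level coefficients if the within-state ICC is above 0.

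It would go too far to say that the intervals will be too narrow, or that chance differences will be reported as effects of law. The ICC, the number of states represented and the variance method are all unstated. The effect is negligible at an ICC near 0.01 with 50 states (about 6% instead of 5%) and large at 0.10 with 20 states (29-34%). Nor is the power statement wrong on its own terms, since it does not say that its groups are defined by state. If they were, pooled-test power at a difference of 0.176 would fall from 79% to 75-51% (50 states) or 70-32% (20 states) over ICC 0.01-0.10.

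**What to change.** Add to Section 11.2, unless the SAP already specifies it: *Models containing a covariate measured at state level will include a random intercept for state; where this is not used, standard errors will be clustered by state with a small-sample correction that is valid when few states are exposed.* The random intercept is preferred because plain clustering broke down with few exposed states. Report beside each such coefficient the number of states represented and the number exposed.

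The cost is one sentence and one model option, using a state identifier already collected. Intervals for state-level factors widen by about √DE: 1.04 to 1.38 times with 50 states (√1.09 to √1.90) and 1.11 to 1.84 times with 20 (√1.24 to √3.40) over the assumed ICCs. Random-intercept odds ratios are conditional on state, which the report should say.
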